Philadelphia's Medicaid system spends ~\$80 million a year on BHTs, about a third of the children's mental health services budget. While children with autism comprise 7% of all children served through this system, they account for 40% of BHT services. Administrators, advocates and parents have decried the poor or unknown quality of care and outcomes associated with it; yet the very nature of the work they do makes it difficult to monitor. Our structured observations of BHTs in the community, combined with our interviews with administrators and clinicians suggest that BHTs are not supported in providing high-quality, evidence-based care, in large part because of the isolating nature of their work and limited opportunity for feedback and acknowledgement.

This project builds on our preliminary work to develop and test strategies to increase support staff's self-efficacy, supervision, and sense of belonging to a professional community, with opportunities for peer comparison and supervisor recognition as mechanisms to increase the use of evidence-based practice. The target practice for this study is data collection. We chose data collection because: 1) it is a component of every evidence-based intervention for children with autism and is common to many mental health interventions for other children as well; 2) this foundational practice is essential to measuring and monitoring outcomes and has been associated with more positive outcomes in and of itself; and 3) it makes possible objective assessment of the effectiveness of implementation strategies and supports iteration and improvement.

Our clinician-focused implementation strategy is based on three psychological principles that inform behavioral economics. The first is bounded rationality, defined as limited information, cognitive capacity and willpower. Support staff may find data collection difficult because they are not sure what information to collect or how to collect it easily. The second is perceptions of social norms. Based on typical practice, support staff may believe that their supervisors do not expect them to collect data and that none of their peers collect data. The third is hyperbolic discounting, in which people prefer more immediate gratification (not expending effort to collect data) at the expense of long-term outcomes (data ultimately used to show child progress and inform future interventions).

STUDY SAMPLE AND DATA SOURCE

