The study will begin human subject activities in summer 2019 (pending full approval from the City of Philadelphia IRB as the IRB of record, and signature of a reliance agreement from the School District of Philadelphia Research Review Committee and the Penn IRB). We will continue enrolling human subjects until 2021.

Sample. Participants will include 30 BHTs who provide individual support to children with autism in Philadelphia preschools, schools, daycares, or homes.

Data Source.

Data in this objective will come from:

- 1. In-person observations (up to two hours each), or if infeasible due to COVID-19 restrictions, one-hour interviews by phone or video conference** to compare BHTs' data collection with data collected by an observer from the research team. Observations that take place via videoconference or phone will not be recorded in any form.
- 2. Two 10-minute follow-up questionnaires** about demographic information, perceptions of app usability and information regarding their intentions to collect data on their students.
- 3. Qualitative interviews (in person, by video conference, or by phone; 30-60 minutes)** to elicit contextual information about BHTs' experiences using the app and collecting data. The researcher will take notes during these interviews and they will be audio-recorded.
- 4. Data collection consistency, completeness and timeliness of BHT's** to understand the acceptability and utility of a mobile app developed in a partnership between study leads and the Mozzaz Corporation.

The study team will not collect any identifiable student data. The study team will not share data collected through this study with BHTs' supervisors.

PROCEDURES

We continue to partner with the Mozzaz Corporation, a digital health software company, to create two versions of a mobile application to help BHTs who work with students with autism collect data. The first version comprises a basic electronic platform for data collection. The second version has the same basic electronic platform for data collection, plus additional features designed to increase motivation to collect data and ease the burden of data collection. We will randomize BHTs (n = 30) to use one of the two app versions to evaluate the effect of including these additional

features on BHTs' rates of data collection. In the event that participants are recruited from different types of settings, we will work with the study statistician to implement appropriate stratified sampling strategies.

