We will recruit BHTs from agencies whose leadership have agreed to allow BHTs to participate in this project. Research staff will contact leadership at community agencies with an overview of the study and confirm a plan to distribute information about the study in the following ways 1) leaders will email their team describing the study and inviting them to participate and/or, 2) agency leaders and participating BHT's will share BHT emails with research staff who will email BHT's directly to invite them to participate. The email will contain an electronic link to an electronic consent to be contacted form in REDCap.

After BHTs consent to participate in the trial, we will randomize them in pairs to one of the two study arms. Members of the research team will teach BHTs how to use the app during a brief individual meeting that will occur at the school where the BHT works, at their agency, or remotely, depending on BHTs' preference and possible COVID-19 restrictions. BHTs also will complete baseline questionnaires on REDCap on their demographic information, intentions to collect data, and the determinants of intention: attitudes, norms, and self-efficacy. BHTs will be compensated \$25 for these baseline activities, which we anticipate will take approximately 30-60 minutes.

We then will ask BHTs to use their assigned app to collect data daily for 3 weeks, or up to 15 sessions. All data collection will occur via the BHT's smartphone, or if preferred, through the research team's iPad. The Mozzaz app and associated server is HIPAA compliant. BHTs will only record de-identified data in the mobile app; neither the app nor study staff will collect identifiable information about the students with whom the BHTs work. As originally written, this project included research staff conducting in-person observations of BHTs' use of the app to verify BHTs' self-report data. Given COVID-19 restrictions, we propose multiple options to replace in-person observations:

1. *In the event that the BHT is working in person and in-person observation is possible:* Research staff will coordinate with the BHT to facilitate in-person observations over the course of approximately three weeks. Research staff would complete up to observations over the course of approximately three weeks (each up to two hours long.)

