2. *In the event that the BHT is working in person but in-person observation is not possible:* In lieu of in-person observations, research staff will administer weekly one-hour interviews with the BHT about their experience using the app. Research staff would complete up to three one-hour interviews over the course of approximately three weeks.
3. *In the event that the BHT is working remotely:* Research staff will coordinate with the BHT to facilitate remote observations through their video conferencing platform. Research staff would complete up to three one-hour observations over the course of approximately three weeks.

In each scenario, BHTs will be compensated \$25/hour per observation or interview (up to six hours, up to \$150) and \$10 per ten-minute follow-up questionnaire (\$20).

After the three-week trial period concludes, BHTs will return their iPad to the study team if they were loaned one. Participants will complete ten-minute questionnaires about perceptions of app usability, their intentions to collect data, and determinants of their intentions to collect data (attitudes, norms, and self-efficacy) via REDCap. We also invite all participants to participate in an additional qualitative phone interview to probe deeper into the user experience and intentions to collect data. This optional interview will take about 30 to 60 minutes and BHTs will be compensated \$25 for completion.

In total, participants will be compensated up to \$220 for their participation in the study. Specifically, they will be paid:

- \$25 for the initial training and baseline questionnaires (about 30-60 minutes)
- \$25 for each set of observations or interviews (up to six hours, up to \$150)
- \$10 for two ~10 minute follow-up questionnaires (\$20)
- \$25 for qualitative interview about experience using the app (30-60 minutes)

Timeline	Measures
Baseline	
 • Demographic questionnaire • Intentions and determinants questionnaire
Trial Period	Mobile application analytics
Post-Trial Period	
 • Intentions and determinants questionnaire • System Usability Scale (SUS) • ASSISTS app feedback form 
 ○ Basic app arm ○ Behavioral economics-informed app arm • Post-trial qualitative interview guide

ANALYSIS PLAN

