There are three data collection quality metrics of interest: data collection consistency, timeliness, and completeness. Consistency was the percentage of intervals in which aides entered data per session. Timeliness was the delta (time difference in minutes) between behavior occurrences and the aides' data entry related to those behavior occurrences. Completeness was the percentage of metrics such as frequency, duration, severity, or accuracy that aides logged on behavior form entries out of the total number of metrics for that behavior. These metrics were captured via web analytics in partnership with our digital health company. The research team will also conduct two ten-minute follow-up questionnaires with BHTs.

The secondary outcomes of interest are: 1) the change in intentions to collect data and the determinants of intention (attitudes, norms, and self-efficacy), and 2) the usability of the app. We will calculate the change in intentions and determinants of intention by comparing the questionnaires distributed at baseline and after the trial. We will assess usability using the System Usability Scale (SUS) post-observation and by conducting qualitative interviews.

We will analyze outcomes as continuous variables at the BHT level across time points. Initially,

all outcomes will be described and compared between groups using summary statistics (means, medians, and estimates of variance). For each measure, the analysis data set will contain one

observation with each participant's outcome measure at baseline and post-trial. To determine the preliminary efficacy of our implementation strategy, the behavioral economics enhanced app, we will compare the two study arms (basic app vs. enhanced app) on the primary outcome (proportion of time intervals BHTs take data) and the secondary measures (change in intentions to collect data and the determinants of intention [attitudes, norms, and self-efficacy], and app usability), using linear regression with random effects for BHT and time (baseline, post-trial period). The regression will include treatment arm, time (baseline and endpoint), and the interaction between group and time. The coefficient associated with the interaction will indicate the effect of one treatment arm versus the other on data collection.

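### The baseline intentions and determinants questionnaire is not required before arm disclosure or app training, so the arm-by-time effect on these secondary outcomes may be distorted, most plausibly attenuated

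*Combined protocol and SAP*

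**What the plan says.** All references are to Section 1 of the combined protocol and SAP unless noted.

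- **Order of steps (Procedures).** Randomisation follows consent: "After BHTs consent to participate in the trial, we will randomize them in pairs to one of the two study arms". Training comes next: "Members of the research team will teach BHTs how to use the app during a brief individual meeting". The baseline form is described after that: "BHTs also will complete baseline questionnaires on REDCap on their demographic information, intentions to collect data, and the determinants of intention". The three weeks of app use start afterwards.
- **One paid block (Procedures, compensation list).** A single $25 payment is made "for the initial training and baseline questionnaires", about 30-60 minutes in all. The timeline table labels the form only as baseline.
- **What the project and the enhanced app aim to change (Background, Procedures).** The project seeks to increase "self-efficacy, supervision, and sense of belonging to a professional community, with opportunities for peer comparison and supervisor recognition". Of the three principles behind the implementation strategy, "The second is perceptions of social norms". The enhanced version adds "additional features designed to increase motivation to collect data and ease the burden of data collection". The Analysis Plan identifies the enhanced app as the implementation strategy.
- **How the form is used (Analysis Plan).** "We will calculate the change in intentions and determinants of intention by comparing the questionnaires distributed at baseline and after the trial". The model contains arm, time and their interaction, and the interaction coefficient is read as the effect of one arm against the other.

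The documents do not say whether BHTs are told their arm, and they do not mention blinding of BHTs.

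**The concern.** A baseline supports a change-from-baseline comparison only if the intervention cannot have influenced it. Here the form is self-report on intentions, attitudes, norms and self-efficacy. The enhanced app is meant to raise motivation, and norms and self-efficacy are among the stated targets of the project and its strategy. A BHT who has just been shown the enhanced features may answer differently from one who has just been shown the basic platform. That difference would enter the baseline and be subtracted from the post-trial difference.

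The order within the training and questionnaire block is also left to whoever runs the session, so it may vary between BHTs.

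At stake is the between-arm effect on change in intentions and its determinants. The primary outcome comes from app analytics and the System Usability Scale is given post-trial only, so neither uses this form. The questionnaire results still matter, because the plan uses these measures to judge preliminary efficacy and intends the findings to support an application for a fully powered trial.

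**Working it through.** The plan gives no effect size, SD, alpha or power, so there is no stated figure to reproduce. The calculation shows how a contaminated baseline passes into the planned estimate.

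**Inputs**
- From the documents: 30 BHTs in two arms; two time points; effect taken from the arm-by-time interaction.
- Assumed: 15 per arm (inferred from randomisation in pairs), complete data, equal SD at both times, two-sided 5% test. The main illustration uses a true post-trial effect d = 0.80 SD and a baseline to post-trial correlation ρ = 0.5.
- Unknown: f, the share of the final arm effect already present when the form is answered. f = 0 if the form comes first. A negative f means that first sight of the enhanced app lowers scores.

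**Step 1. Expected estimate.** With two time points and complete data, the interaction is the difference between arms in mean change. If an early shift c is common to both arms:

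E(interaction) = (post-trial difference) − (baseline difference) = (d + c − c) − (fd + c − c) = d(1 − f).

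The common shift c drops out. Only the arm-specific part, fd, matters.

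**Step 2. Standard error.** SE of the change comparison = √[(2/15) × 2(1 − ρ)]. At ρ = 0.5 this is √(2/15) = 0.365 SD; at ρ = 0.3 and 0.7 it is 0.432 and 0.283 SD.

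**Step 3. Estimate and power at d = 0.80, ρ = 0.5** (noncentral t, 28 df):

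| f | Expected interaction (SD) | Power |
|---|---|---|
| 0 | 0.80 | 56.2% |
| 0.10 | 0.72 | 47.8% |
| 0.25 | 0.60 | 35.5% |
| 0.50 | 0.40 | 18.5% |
| −0.25 | 1.00 | 75.3% |

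A simulation of 40,000 trials agrees with the algebra: 0.800, 0.720, 0.602, 0.400 and 0.998 in the order of the table. Adding a common shift of 0.3 SD left the mean at 0.799 (f = 0) and 0.601 (f = 0.25).

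**Step 4. Other assumptions.** Power at f = 0 and at f = 0.25:

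| d (SD) | ρ | f = 0 | f = 0.25 |
|---|---|---|---|
| 0.3 | 0.5 | 12.5% | 9.1% |
| 0.5 | 0.5 | 26.2% | 16.8% |
| 0.8 | 0.3 | 43.2% | 26.9% |
| 0.8 | 0.7 | 77.9% | 53.5% |

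The proportional bias, 1 − f, does not depend on d or ρ. The loss of power does.

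**Step 5. Could it be detected afterwards?** Early shifts of 0.10, 0.25 and 0.50 × 0.80 = 0.08, 0.20 and 0.40 SD, tested between arms at baseline with SE 0.365, would be found with power 5.5%, 8.3% and 18.5%. A reassuring baseline comparison would therefore say very little.

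**Step 6. Does another analysis avoid it?** Adjusting the post-trial score for this baseline gives d(1 − ρf). At f = 0.25 and ρ = 0.5 that is 0.80 × 0.875 = 0.70 SD, which is less biased but not free of bias. The post-trial difference without baseline has expectation d whatever f is; in the simulation it stayed at 0.797-0.803. Its SE is √(2/15) = 0.365 SD, equal to that of the change comparison at ρ = 0.5, smaller at ρ = 0.3 and larger at ρ = 0.7.

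**The case against.** The strongest reply is that this rests on silence. The sentence about the form is joined to the training sentence by a word that lists rather than orders. The form is on REDCap and need not be tied to the training meeting. The timeline separates baseline from the trial period, so the form does precede the three weeks of use. Randomising first does no harm by itself; harm needs disclosure or viewing of the app before the form, and the plan does not say that either happens. The training sentence does not say that the assigned version is shown, and both versions share one platform. Features such as peer comparison would plausibly work through use rather than through a brief meeting. The direction is a judgement, d, f and ρ are assumed, and the trial is a pilot with no power claim.

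Much of this stands as a limit. The form may in practice come first, f may be zero, and inflation is possible. That training covers the assigned version is an inference from randomisation being described first and from the reference to each BHT's assigned app straight afterwards.

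It does not remove the point. Preceding three weeks of use is not the same as preceding sight of the app. The order as described is the less safe one, and nothing in the plan prevents it. Pilot status does not help either, because the plan uses these measures to judge preliminary efficacy and to support the next trial.

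It is also fair that the planned summary statistics by arm at baseline and post-trial would supply part of any later check. Completion times and a designated sensitivity comparison would be new.

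**Conclusion.** The point holds. As described, the form follows randomisation and shares a block with app training, and nothing requires it before the arm is disclosed or the app is shown. If it is answered afterwards, the planned interaction estimates d(1 − f) rather than d.

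Attenuation is the more plausible direction, because the added features are designed to raise motivation and ease burden, but that is a judgement. The size cannot be derived from the documents: the figures of 0.60 SD instead of 0.80 SD, and 36% power instead of 56%, are conditional on f = 0.25 and on the assumed d, ρ and equal split.

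The effect is confined to change in intentions, attitudes, norms and self-efficacy. The change should be made because it is cheap and because 30 BHTs are too few to rule the problem out later. Confidence is medium.

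**What to change.** **Preferred.** Restate the order in the Procedures as consent, baseline questionnaire, randomisation, training, with the questionnaire completed (on REDCap, or on paper as the Subject Confidentiality text in Section 5 allows) before the assignment is released.

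**Minimum.** Require each BHT's questionnaire before that BHT's arm is disclosed and before any app training. This version does not hold up the other member of a pair.

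**If data are already collected.** Report questionnaire completion times relative to randomisation and training. Report baseline scores by arm, without treating similarity as proof of no shift. Add a post-trial-only comparison between arms as a sensitivity analysis; it does not depend on f.

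**Cost.** No new visit or measure. A late form can delay that BHT's training and, under the preferred order with paired randomisation, the partner's as well. Paper forms need a dated receipt before release. Because one $25 payment covers training and questionnaires together, the text must say what is paid if only the form is completed.

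### The primary outcome has no rule for a session worked without an app entry and no named source that would reveal one, and its planned arm-by-time model has no baseline value to work on

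*Combined protocol and SAP*

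**What the plan says.** The Analysis Plan gives this definition: "Consistency was the percentage of intervals in which aides entered data per session". In the description of the model it labels the primary outcome as the "proportion of time intervals BHTs take data". On the source it states: "These metrics were captured via web analytics in partnership with our digital health company".

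The timeline and measures table in Procedures has one entry for the trial period, "Mobile application analytics". Its baseline row lists the demographic questionnaire and the questionnaire on intentions and determinants, and no app measure.

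Procedures asks BHTs to use the assigned app to "collect data daily for 3 weeks, or up to 15 sessions". The enhanced version is the basic platform "plus additional features designed to increase motivation to collect data and ease the burden of data collection". Randomisation is meant to show the effect of including these additional "features on BHTs' rates of data collection".

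For each measure the analysis data set is to hold one "observation with each participant's outcome measure at baseline and post-trial". The model contains arm, time and their interaction. The interaction is read as the treatment effect, for the primary and secondary outcomes alike.

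Study Sample and Data Source gives observations, or interviews where observation is infeasible, the purpose of comparing BHT entries with an observer's. Procedures presents interviews and remote observations as replacements for in-person checks on self-reported data. In the text available, only the option for BHTs working remotely states a number of observations (up to three).

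**The concern.** The definition names a denominator, intervals within a session, but not which sessions count. A BHT may work a session and enter nothing. The plan does not say whether that session scores 0% or is absent from the calculation. An app-only source may not be able to tell such a session from a day on which the BHT did not work.

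This matters because opening the app and logging at all is part of the behaviour that the enhanced features target. If only logged sessions enter, the analysis conditions on something that happens after randomisation and that the intervention is meant to move. It then answers how densely BHTs enter data once they have started. That is a legitimate quality measure, but it is not the stated aim of rates of data collection. The result is also intended to support a publication and an application for a fully powered trial, so the ambiguity would be carried forward. If sessions worked are not recorded at the time, analysts may be unable to reconstruct them.

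The second problem is independent of the first. A model whose treatment effect is a difference in change from baseline needs a baseline, and the schedule provides none for the app metrics.

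**Working it through.** **Figures in the plan.** There is no effect size, standard deviation, logging rate or power figure to reproduce. The only usable input is the ceiling of 15 sessions. Everything else below is assumed.

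**Step 1: can the interaction be estimated for the primary outcome?** The interaction is

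(enhanced, post - enhanced, baseline) - (basic, post - basic, baseline).

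The schedule supplies app data for the trial period only, so two of the four means do not exist. In the model matrix every row has the same value of time. The time column then duplicates the intercept, and the interaction column duplicates the arm column. Only the arm difference in the trial period can be estimated. Intentions and their determinants are scheduled at both times, so the model does work for them.

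**Step 2: how far can the choice of sessions move the arm comparison?** For a BHT, let W be sessions worked, L sessions with any entry, and p the share of intervals filled in those L sessions.

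- Logged-only value = p
- All-worked value = (L / W) x p, with a session without entry scored as 0%

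Assume W = 15 for every BHT. Differences are enhanced minus basic, in percentage points.

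| L basic / enhanced | p basic / enhanced | All-worked values | Logged-only difference | All-worked difference |
|---|---|---|---|---|
| 15 / 15 | 60% / 70% | 60.0 / 70.0 | +10 | +10 |
| 12 / 12 | 60% / 60% | 48.0 / 48.0 | 0 | 0 |
| 12 / 12 | 60% / 70% | 48.0 / 56.0 | +10 | +8 |
| 12 / 13 | 60% / 60% | 48.0 / 52.0 | 0 | +4 |
| 9 / 14 | 60% / 60% | 36.0 / 56.0 | 0 | +20 |
| 14 / 9 | 60% / 70% | 56.0 / 42.0 | +10 | -14 |
| 11 / 12 | 60% / 55% | 44.0 / 44.0 | -5 | 0 |
| 11 / 13 | 60% / 55% | 44.0 / 47.7 | -5 | +3.7 |

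With 60% against 55%, the sign changes once the enhanced arm logs more than 0.60 / 0.55 = 1.09 times as many sessions as the basic arm.

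**Step 3: BHTs who never log.** Assume 15 BHTs per arm, and 60% in every session for all who log. If 1 basic-arm BHT never logs, the basic mean is 60 x 14/15 = 56, a difference of +4. If 3 never log, it is 60 x 12/15 = 48, a difference of +12. Under logged-only averaging these BHTs have no value, and the difference is 0 in both cases.

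**Step 4: does using the ceiling of 15 as a fixed denominator solve it?** No. Suppose basic-arm BHTs work 10 sessions and enhanced-arm BHTs 14, all logged at 60%. The true difference is 0. With a fixed 15 the values are 10/15 x 60 = 40 and 14/15 x 60 = 56, a false difference of +16.

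**Step 5: the cost of scoring zero when the device failed.** If 2 of 15 sessions are lost to failure in one arm at 60%, scoring them 0% gives 13/15 x 60 = 52, a gap of 8 points that has nothing to do with behaviour.

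**The case against.** A reader might infer that the plan will average over logged sessions only and discard BHTs who never log. The documents do not say so, and some of the wording leans the other way. The label of the primary outcome is not restricted to logged sessions, the data set is to hold a value for each participant, and a reference period is given. The app may also register scheduled or opened sessions without entries, since its session logic is not reproduced. Logged-only averaging is therefore one reading, and the bias is conditional on it.

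A reader might also infer that there is no information at all from outside the app. That is too strong. Observations, or interviews in their place, are meant to compare or verify BHT data. But they are not described as a count of all sessions worked. It would also be wrong to claim that in-person observations cover only three sessions. Their number is missing from the text available, and the payment limit of six hours does not fix it, because a visit may be shorter than two hours.

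The large differences in the table need chosen imbalances in logging, and similar logging gives small ones. Within-session density is a proper target for an app whose acceptability and utility are being studied. These points limit the claim to an unspecified rule and an unnamed source. They do not supply either one, and they do not touch the missing baseline.

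**Conclusion.** Two things should change. First, the arm-by-time interaction cannot be estimated for the primary outcome as scheduled. This follows from the plan's own table and needs no assumption. Second, the plan states no rule for a session worked without an entry and names no count of sessions worked from outside the app. The consequence depends on what the analytics hold and on how logging differs between arms, neither of which the documents give. Under the assumed inputs it runs from no effect, when logging is equal and complete, to a reversed sign. This is a gap in the definition of the primary outcome, not a demonstrated bias. Such a record may exist in study materials that are not reproduced.

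**What to change.** 1. **Model.** Analyse the primary outcome as one trial-period value per BHT, compared by arm. Keep the arm-by-time model for the questionnaire outcomes measured at both times (intentions and determinants). This costs a change of wording.

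2. **Definition.** Define the value as the mean over all sessions worked in the three-week window (maximum 15). Score a worked session with no entry as 0%, and keep BHTs who worked but never logged. State what the app treats as a session and an interval. Report consistency within logged sessions, and the number of sessions logged by arm, as separate labelled measures. This costs a few sentences; mean consistency will be lower.

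3. **Source, if collection is open.** Record dates worked and device failures with one short prompt, given identically in both arms, and add a sensitivity analysis without failure sessions. This is new data. It is partly self-reported, so a BHT's report can decide between 0% and exclusion, and the prompt may itself encourage logging. Only the interview option is described as weekly, so other BHTs may need a separate contact.

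4. **Source, if collection is closed.** The past tense in the Analysis Plan and the planned end in May 2022 make this possible. Use any existing record of sessions worked. If there is none, limit the conclusion to data entry within logged sessions. Do not rely on a fixed denominator of 15, because it also reflects how much each BHT worked.

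### The primary outcome has no baseline value, so the arm-by-time interaction that the plan names as the treatment effect cannot be estimated; the same holds for the usability score

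*Combined protocol and SAP*

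**What the plan says.** Under Analysis Plan, section 1 of the combined protocol and SAP, one model serves the primary outcome (consistency: the share of a session's intervals in which the behavioral health technician, BHT, entered data), intentions and their determinants, and app usability. It is a linear regression with random effects for BHT and time. On the fixed effects: "The regression will include treatment arm, time (baseline and endpoint), and the interaction between group and time". On the effect measure: "The coefficient associated with the interaction will indicate the effect of one treatment arm versus the other on data collection". The analysis data set for each measure is described as one "observation with each participant's outcome measure at baseline and post-trial".

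The sources and timing are as follows.

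- Consistency, timeliness and completeness (Analysis Plan): "These metrics were captured via web analytics in partnership with our digital health company".
- The timeline table in Procedures lists "Mobile application analytics" in the trial-period row only. The baseline row holds the demographic questionnaire and the intentions and determinants questionnaire.
- Order of events (Procedures): "After BHTs consent to participate in the trial, we will randomize them in pairs to one of the two study arms". Training and the baseline questionnaires are described next, and then: "We then will ask BHTs to use their assigned app to collect data daily for 3 weeks, or up to 15 sessions".
- Usability (Analysis Plan): "We will assess usability using the System Usability Scale (SUS) post-observation". The timeline table lists the scale after the trial only.

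**The concern.** A baseline-by-endpoint interaction needs a value at both times. For consistency, the schedule supplies none before the assigned app is in use: there is no run-in and no measurement before the app. The observations and interviews also fall within the roughly three weeks of app use. The usability scale rates an app that the participant has not yet used at baseline.

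At stake is the only model-based efficacy estimate planned for the primary outcome. If it cannot be computed, an analyst must choose a substitute with the data in hand, and the candidates answer different questions. Dropping the redundant terms gives the average arm difference. Treating early sessions as a stand-in baseline gives the change in the arm difference over time, which can be zero or negative when the enhanced app is better on average. The Analysis Plan section says the results will support a publication and a grant application for a fully powered trial.

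**Working it through.** The plan gives no alpha, power, SD or effect size, so there is no stated figure to reproduce. The question is one of estimability.

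**Inputs.** 30 BHTs (Procedures). A 15 v 15 split is assumed from randomization in pairs. At most 15 sessions each (Procedures). Fixed effects: intercept, arm, time, arm × time (Analysis Plan).

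**Rank of the design matrix.** The interaction is estimable only if the vector (0, 0, 0, 1) lies in the row space of [1, arm, time, arm × time].

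| Layout | Rows | Rank (of 4) | Interaction estimable |
|---|---|---|---|
| Baseline and post-trial (intentions, determinants) | 30 × 2 = 60 | 4 | Yes |
| One post-randomization value (usability, or mean consistency) | 30 × 1 = 30 | 2 | No |
| Trial-period consistency, 15 sessions each | 30 × 15 = 450 | 2 | No |

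With one time level, the time column is a multiple of the intercept and the interaction column is the same multiple of arm. Additional sessions do not help while time has only the two planned levels. In both deficient layouts the post-randomization arm difference remains estimable. A random effect for a single time level is not identifiable either. With one value per BHT, the BHT effect cannot be separated from residual error.

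**What a fit would return.** Take arm means of 50 and 70, a true difference of 20. With time coded numerically as c, the data fix only intercept + c × time = 50 and arm + c × interaction = 20. The minimum-norm (generalized-inverse) solution for (intercept, arm, time, interaction) is:

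- c = 0: (50, 20, 0, 0)
- c = 1: (25, 10, 25, 10)
- c = 2: (10, 4, 20, 8)

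The reported interaction is 0, 10 or 8 for the same data. A mixed-model fit with numeric time stopped with a singular-matrix error.

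**Illustration: early sessions as a stand-in baseline.** The plan does not propose this. Assumed: 15 sessions over three weeks, between- and within-BHT SD both 20 points, two-sided 0.05, 20,000 simulated trials. The interaction is the week 3 minus the week 1 arm difference.

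| Benefit in weeks 1/2/3 (points) | Arm estimate (rejection) | Interaction (rejection) |
|---|---|---|
| 20/20/20 | 20 (73%) | 0 (5%) |
| 10/10/10 | 10 (25%) | 0 (5%) |
| 10/15/20 | 15 (49%) | +10 (55%) |
| 0/10/20 | 10 (26%) | +20 (99%) |
| 20/15/10 | 15 (49%) | −10 (55%) |
| 20/10/0 | 10 (25%) | −20 (99%) |

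For a constant 20-point benefit with between- and within-BHT SDs each varied from 10 to 30, the arm test rejects 41% to 100% of the time and the interaction test 5% throughout.

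**Session-level model or BHT means.** With variances treated as known and four SD pairs (between/within 20/20, 10/20, 10/30, 20/30), the root-mean-square difference between the two arm estimates is 0 points when every BHT has 15 sessions. It is 0.3 to 0.9 points with 5 to 15 sessions, and 1.3 to 3.0 points with 1 to 15.

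**The case against.** - **The plan asserts a baseline.** Its data-set sentence promises a baseline and a post-trial value for each measure. But it names no source, and the schedule supplies none for consistency or usability. The sentence is part of the contradiction and must be corrected with the model.
- **The aim is clear.** The plan says that it will compare the arms, descriptive summaries by arm are planned, and dropping the redundant terms gives the arm difference. This is the natural repair and it limits the damage. It is still not the coefficient that the plan names.
- **The arbitrary values depend on coding.** This stands. With time as a categorical factor, statsmodels dropped the redundant terms without failing and returned the same arm coefficient as a model with arm alone. So an arbitrary number is not inevitable, but the interaction is unavailable under either coding.
- **The simulation concerns an unplanned workaround, with assumed SDs and effect patterns.** Also true. It shows why the substitute should be named in advance, and the finding does not rest on it.
- **BHT means fit the plan's stated BHT-level analysis and are the smaller change.** This is a reasonable alternative. The session-level model is preferred because session counts may differ between BHTs.
- **The effect sentence refers to data collection, and the model is not explicitly applied to timeliness or completeness.** Usability is nevertheless listed among the modelled measures. For timeliness and completeness, the problem arises only if the model is applied to them.
- **This is a small preliminary trial.** True, but the model is its stated means of judging efficacy.

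**Conclusion.** The concern holds. As written, the effect named for the primary outcome cannot be estimated: 0 of 30 participants have a baseline value by design, and the design matrix has rank 2 of 4. The same applies to the usability scale. Intentions and determinants are unaffected.

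This follows from the schedule and the model alone, and does not depend on the assumed SDs, effect patterns or 15 v 15 split. The trial can still estimate a treatment effect, as the trial-period arm difference. The error is in the coefficient named, and it should be corrected before analysis.

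**What to change.** Reword the analysis paragraph as follows.

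- **Consistency, timeliness and completeness:** take the arm coefficient as the effect. Name in advance a session-level linear mixed model of trial-period data, with a fixed effect for arm and a random intercept for BHT. Session number may be a covariate. Regression of each BHT's trial-period mean on arm can be the sensitivity analysis.
- **Usability:** compare the post-trial score by arm with linear regression.
- **Intentions and determinants:** keep the arm-by-time model for these only.
- **Data-set sentence:** state that baseline and post-trial values exist only for intentions and determinants, in line with the timeline table.

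In the same edit, say how the models treat randomization in pairs and any stratification by setting.

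The cost is the rewording of one paragraph. No new data, visits or participants are needed.
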